9.3 Exclusion criteria

1. Woman who is pregnant or lactating, or pre-menopausal woman who is sexually active and not using a reliable method of contraception (see section 11).
2. Clinically relevant abnormal medical history, physical findings, ECG, or laboratory values at the pre-trial screening assessment that in the opinion of the

investigator could interfere with the objectives of the trial or the safety of the volunteer.

3. Presence or history of acute or chronic illness sufficient to invalidate the volunteer's participation in the trial or make it unnecessarily hazardous.
4. Presence or history of respiratory disease, including (but not limited to) asthma, chronic obstructive pulmonary disease (COPD), cystic fibrosis, emphysema, requiring acute or chronic medication.
5. Presence of nasal polyps or significant nasal abnormalities.
6. Symptoms of respiratory illness (including, but not limited to, runny nose, sore throat, sneezing, coughing or wheezing) at the screening visit or before dosing on Day 1.
7. Tympanic temperature $> 37.5^{\circ}\text{C}$ at the screening visit or before dosing on Day 1.
8. Impaired endocrine, thyroid, hepatic, respiratory or renal function, diabetes mellitus, coronary heart disease, or history of any psychotic mental illness.
9. History of psychiatric disease, as determine by the investigator.
10. History or presence of malignant disease.
11. Immune-suppressed status, resulting from either disease or medication, as determined by the investigator.
12. Presence or history of severe adverse reaction to any drug or the excipients of Neumifil.
13. Known allergy to tetracycline antibiotics.
14. Use of a prescription medicine (except HRT in female subjects), including oral contraceptives, during the 28 days before the first dose of trial medication, or use of an over-the-counter medicine, with the exception of acetaminophen (paracetamol) and vitamin or nutritional supplements, during the 7 days before the first dose of trial medication.
15. Receipt of an investigational product (including prescription medicines) as part of another clinical trial within the 3 months before admission to this study; in the follow-up period of another clinical trial at the time of screening for this study.
16. Receipt of a COVID-19 vaccine within 7 days before the first dose of trial medication, or anticipate receiving a COVID-19 vaccine within the 7 days after a (final) dose of trial medication.
17. Presence or history of drug or alcohol abuse, or regular intake of more than 14 units of alcohol weekly.
18. Use of cigarettes or nicotine-containing products during the 6 months before first dose of trial medication.

19. Blood pressure and heart rate in supine position at the screening examination outside the ranges: blood pressure 90–140 mm Hg systolic, 40–90 mm Hg diastolic; heart rate 40–100 beats/min. Triplicate measurements will be made (at least 2 min apart), and a mean value outside the above ranges will lead to exclusion.

Repeat measurements (in triplicate) are permitted if values are borderline (ie values that are within 5 mm Hg for blood pressure or 5 beats/min for heart rate) or if requested by the investigator. Subjects can be included if the repeat value is within range or still borderline but deemed not clinically significant by the investigator.

20. QTcF value, of > 450 msec (men) or > 470 msec (women); or QRS duration \geq 120 msec, measured on 12-lead ECG at the screening visit. Triplicate measurements will be made, and a mean value used to determine eligibility. A repeat (in triplicate) is also allowed on one occasion for determination of eligibility.

21. Possibility that the volunteer will not cooperate with the requirements of the protocol.

22. Positive test for hepatitis B surface antigen, hepatitis C or HIV. NOTE: participants with positive hepatitis C antibody owing to resolved disease can be included only if a hepatitis C ribonucleic acid (RNA) test is negative.

23. Positive test for SARS-CoV-2 (polymerase chain reaction; PCR) or suspected exposure to the SARS-CoV-19 virus during the 14 days before screening.

24. Loss of more than 400 mL blood during the 3 months before the trial, eg as a blood donor.

25. Objection by GP to volunteer entering trial.

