7.1.2 Exploratory objective

- To determine the number of subjects contracting SARS-CoV-2 during the 7 days after receiving their (last) dose.
- To assess the formation of Neumifil ADAs after multiple-ascending intranasal doses in healthy subjects (Part B only).

- To assess the plasma concentration of single- or multiple-ascending intranasal doses of Neumifil in healthy subjects to determine if intranasal administration results in systemic exposure.
- To assess the concentrations of cytokines and chemokines in nasal secretions before dosing and after multiple intranasal doses of Neumifil (Part B only).

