7.2.2 Exploratory endpoint

Safety: SARS-CoV-2 infection test, done at screening, before the first dose, on Day 8 (Part B only), and at follow-up.

Immunogenicity: ADAs of Neumifil, as assessed by IgA and IgG concentration, derived from blood samples taken before the first dose and at Follow-up (Part B only).

Plasma concentration of Neumifil: Plasma concentrations of Neumifil after single doses on Day 1 in Part A, and after dosing on Days 1 and 7 in Part B.

Cytokine and chemokine concentrations in nasal secretions: Presence and concentration of cytokines and chemokines, measured by multiplex assay, in nasal wick samples collected on Day -1, Day 8, and at follow up (Part B only).

8 Overall trial design

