8.1.1 Part A

Enrolment of up to 36 healthy subjects is planned, in up to 5 groups (Groups A1–A5). Groups A1–A3 will consist of 6 subjects each, and Groups A4 and A5 will consist of 9 subjects each.

Subjects will receive a single intranasal dose of Neumifil or placebo. In Groups A1–A3, 4 subjects will receive Neumifil and 2 will receive matching placebo. In Groups A4 and A5, 6 subjects will receive Neumifil and 3 will receive matching placebo. Additional dose levels may be explored in up to 2 optional groups of up to 9 subjects each.

The starting dose for Group A1 is 0.028 mg Neumifil. Subsequent planned doses are given in Table 3.

Table 3 Planned doses in Part A

Group	Planned nominal dose of Neumifil	Number of subjects	Number on placebo
A1	0.028 mg	6	2
A2	0.085 mg	6	2
A3	0.28 mg	6	2
A4	0.885 mg	9	3
A5	2.8 mg	9	3
A6 (optional)	To be decided	9	3
A7 (optional)	To be decided	9	3

Because Neumifil has never been given to humans before, each new ascending dose will be staggered: sentinel subjects will be dosed first, and the remaining subjects will be dosed at least 23 h later. To maintain the blind nature of the study, the 2 sentinel subjects will be randomised to ensure that 1 subject receives active treatment and the other receives placebo. Since 1 subject will receive placebo treatment, the sentinel subjects may be dosed at least 5 min apart. Provided the investigator considers the safety and tolerability in the sentinel subjects to have been acceptable, the remaining subjects will be dosed, at intervals of at least 10 min.

The planned dose levels may be changed, depending on the safety and tolerability results after previous doses, as described in section 8.5. The dose will not be escalated unless the safety and tolerability of the previous dose is acceptable. There will be an appropriate interval between sequential groups, to allow for review of those data. If the dose level selected is no higher than one that has already been shown to cause no safety concerns, sentinel subjects will not be required, and subjects will be dosed at intervals of at least 10 min. The maximum dose will not exceed 2.8 mg.

Subjects will be screened within 35 days before their dose of trial medication.

Subjects will be resident on ward from 1 day before their dose (Day –1) until about 24 h after dosing (Day 2). They will return for a follow-up visit 7–8 days after their dose (Day 8–9).

8.1.2 *Part B*

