12.1 Schedule of procedures

12.1.1 Part A

Period:	Screening 1	Study session											Follow-up			
		Day:	-35 to -2	-1	Pre	0	0.25	0.5	1	2	2.5	3	4	8	12	24
Time (h)																
Informed consent	X															
Inclusion/exclusion criteria	X	X	X													
Medical history	X															
Admission		X														
Inpatient stay			◀											▶		
Discharge																X
Safety assessments																
Physical examination ²	X	X							X							X
Height & weight ³	X	X														X
Vital signs ⁴	X	X	X						X			X	X	X	X	X
12-lead ECG ⁵	X		X							X						X
Serology	X															
Laboratory safety tests ⁶	X	X	X										X		X	X
Pregnancy ⁷	X	X														X
FSH ⁸	X															
Urine drug, alcohol and cotinine tests	X	X														
Spirometry ⁹	X											X	X	X	X	X
Nasal examination	X	X														X
SARS-CoV-2 infection test ¹⁰	X	X														X
Self-assessment nasal tolerability rating scale								X								X
Dosing																
Intranasal Neumifil					X											
Neumifil PK																
PK sampling ¹¹				X					X	X		X				

Abbreviations: ECG: electrocardiogram; FSH: follicle-stimulating hormone; PK: pharmacokinetics; AEs: adverse events.

Notes:

1. Screening will be within 35 days before dosing
2. Full physical examinations will be done at screening and on Day -1. Brief (symptom-directed) physical examinations will be done at all other timepoints.
3. Height measured at screening only.
4. Vital signs consist of: systolic and diastolic blood pressure, heart rate, pulse oximetry, temperature and respiratory rate. They will be assessed at screening; on Day -1, and before and at 2, 4, 8, 12 and 24 h after dosing on Day 1; and at follow-up. Triplicate measurements (at least 2 min apart) will be made at screening and before dosing. Single measurements will be made at all other time points. Measurements should be made with subjects in a supine position, after resting for 5 min.
5. ECGs will be recorded at screening; before and at 2.5 h after dosing on Day 1; and at follow-up. Triplicate recordings (at least 2 min apart) will be made at screening and before dosing; single recordings will be done at all other time points. Recordings should be made with subjects in a supine position, after resting for 5 min.

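### Exclusion criterion 23 counts SARS-CoV-2 exposure back from screening, not from first dose, so a known exposure between the two does not exclude a subject who tests negative on Day -1 and is symptom-free and afebrile on Day 1

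*Combined protocol and SAP*

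**What the plan says.** Section 9.3, criterion 23, has two limbs. One is a positive SARS-CoV-2 PCR. The other is "suspected exposure to the SARS-CoV-19 virus during the 14 days before screening". Section 8.1.1 states "Subjects will be screened within 35 days before their dose of trial medication". Section 8.1.2 gives Part B the same limit, and both schedules in section 12.1 label the screening column Day -35 to Day -2.

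The related COVID-19 vaccination rule, criterion 16, has a different anchor: "Receipt of a COVID-19 vaccine within 7 days before the first dose of trial medication".

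The exploratory objective in section 7.1.2 is "To determine the number of subjects contracting SARS-CoV-2 during the 7 days after receiving their (last) dose". Section 7.2.2 sets the measurement: "SARS-CoV-2 infection test, done at screening, before the first dose, on Day 8 (Part B only), and at follow-up". The schedules place the pre-dose test on Day -1 and mark eligibility checks at screening, on Day -1 and before dosing on Day 1. Criteria 6 and 7 also exclude anyone with respiratory symptoms or a raised temperature before dosing on Day 1.

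**The concern.** An exposure look-back is useful for the days just before dosing, when an infection could be incubating without yet being detectable. Criterion 23 fixes its window at screening, which can be five weeks earlier. Repeating the eligibility check on Day -1 and Day 1 does not move the window, because the wording still points to screening. A subject screened on Day -30 who reports contact with a case on Day -3 meets no exclusion on that account.

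Two things are at stake.

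- **The infection count.** In Part A the next scheduled test after Day -1 is at follow-up on Day 8–9. In Part B it is on Day 8, one day after the last planned dose. A positive result there may reflect an infection acquired before the first dose, and the plan has no rule for dating it.
- **The safety data.** An infection produces nasal and respiratory complaints of the kind the primary objective watches for. Section 14.2 records any nasal questionnaire score above zero as an adverse event. Its definition of a related event also allows for events that have a common alternative explanation. Section 6.5.1 separates vaccination from dosing so that adverse events do not overlap, and the same reasoning applies to an incubating infection.

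**Working it through.** The plan gives no figure of its own to reproduce: section 16.1.2 has no hypotheses and section 16.2 has no sample-size calculation. The check is a day count on the plan's own windows, followed by a rough scale.

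**Inputs**
- Look-back length: 14 days, ending at screening (criterion 23).
- Screening day: Day -g, with g from 2 to 35 (section 12.1), giving 35 - 2 + 1 = 34 permitted days.
- Dosing: Day 1. Section 8.1 describes Day -1 as one day before dosing, so there is no Day 0 and Day -g is g days before dosing.

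**Coverage of the last 14 days before dosing**
1. The window for screening on Day -g runs from g + 1 to g + 14 days before dosing.
2. Its overlap with days 1 to 14 before dosing is max(0, 14 - g).
3. Latest screening, g = 2: 14 - 2 = 12 of 14 days covered.
4. From g = 14 upward the overlap is 0. That is 35 - 14 + 1 = 22 of the 34 permitted days (65%).
5. Earliest screening, g = 35: the window covers days 36 to 49 before dosing.
6. If screening dates were spread evenly (an assumption), mean coverage is (12 + 11 + ... + 1)/34 = 78/34 = 2.3 days, or 2.3/14 = 16%.
7. Anchored to the first dose, coverage is 14 of 14 days whatever the screening date.

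**Weight of one case**
- Groups A1–A3 have 4 active and 2 placebo subjects, A4–A5 have 6 and 3, and B1–B3 have 6 and 2.
- One infected active subject is therefore 1/4 = 25% or 1/6 = 17% of the active subjects in a group.

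**Scale, on assumed risks only**
- Let p be the chance per subject of an infection that is incubating but test-negative on Day -1. The documents give no value for p.
- The chance of at least one such case among n subjects is 1 - (1 - p)^n.

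| Assumed p | Part A, n = 36 | Part B, n = 24 | All, n = 60 |
|---|---|---|---|
| 0.1% | 3.5% | 2.4% | 5.8% |
| 0.5% | 16.5% | 11.3% | 26.0% |
| 1% | 30.4% | 21.4% | 45.3% |
| 2% | 51.7% | 38.4% | 70.2% |

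Here p includes infections from exposures the subject never noticed. The criterion can act only on suspected exposures, so these figures are an upper limit on what re-anchoring could prevent.

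**The case against.** The strongest reply is that other safeguards do most of the work. There is a test on Day -1, eligibility is re-checked on Day -1 and Day 1, and symptoms or fever on Day 1 exclude. The positive-PCR limb is most naturally read as carrying no screening limit. This stands, and it rules out the broader inference that anyone exposed shortly before dosing is eligible. What remains is the subject with a known exposure who passes all those checks.

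A reader might also infer that the plan will credit these infections to Neumifil, or that they bias the comparison. The documents support neither. They contain no rule for dating infections, so how a case would be classified is open. Allocation is randomised and double-blind, so placebo subjects carry the same risk. Nor would a symptomatic case easily pass as a local drug effect: the schedule notes in section 12.1 call for ad hoc tests when symptoms appear, and section 6.5.1 requires COVID-19-related adverse events to be documented.

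Three further replies have some force.
- Anchors are mixed throughout section 9.3. Criteria 14, 16 and 18 use first dose, but 15 uses admission and screening, and 19 and 20 use screening. So criterion 23 is not the only one tied to screening. It is, however, the one whose purpose depends on closeness to dosing.
- The site's COVID-19 risk mitigation policy, cited in section 6.5.1, covers volunteer testing and may include an exposure question at admission. Its content is not in the documents, so it can be neither counted on nor dismissed.
- Re-anchoring leaves unrecognised exposures untouched and does not date a Part A positive found on Day 8–9. That limits the benefit of the change but does not argue for the present anchor.

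**Conclusion.** The point holds as a minor one. Criterion 23 states a look-back that covers 0 to 12 of the 14 days before dosing, and none of them for 22 of the 34 permitted screening days. Those counts depend only on the plan's windows. The 16% mean coverage depends on evenly spread screening dates, and it describes calendar days, not the number of infections missed.

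The consequence is a possible small number of infections, in either arm, that cannot be placed before or after dosing, together with non-drug adverse events in groups of 6 to 9 subjects. How often this would happen cannot be established from the documents.

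A reader might take this as a threat to the trial's main conclusions. It is not shown to be one: the infection count is exploratory, nothing is tested, and no sample size depends on it.

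**What to change.** Amend criterion 23 in four respects:

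1. Count suspected exposure over the 14 days before the first dose, using the anchor that criterion 16 already has.
2. Ask about exposure at the eligibility checks already scheduled on Day -1 and Day 1.
3. State that a positive test at screening or on Day -1 excludes. The current sentence could be read as applying the screening time limit to the test limb as well.
4. Replace SARS-CoV-19 with SARS-CoV-2.

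The cost is one line in an amendment and one question at existing checks. An occasional screened subject will be deferred or replaced. Infections from unrecognised exposure will remain. For those, the statistical analysis plan, which section 16.1.1 says will be prepared before first database lock, could state how a positive at the first post-dose test is classified in each part and give a sensitivity count without such cases. If the site policy already asks about exposure up to admission, a cross-reference in criterion 23 would make that visible.

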9.4 Withdrawal of subjects from the trial

9.4.1 *Withdrawal of subjects*

Subjects are free to withdraw from the trial at any time without giving reasons. Furthermore, the investigator may withdraw a subject for reasons such as intolerance to trial medication, intercurrent illness, need for medication, which is contraindicated, significant non-compliance with the requirements of the trial, or withdrawal of consent. The investigator will assess the reasons for withdrawal as far as possible and will fully record the circumstances and medical details.

9.4.2 *Individual subject stopping criteria (Part B only)*

A subject who meets any of the following criteria will receive no further doses.

- SAE considered related to study treatment.

- alanine aminotransferase (ALT) $\geq 5 \times$ the upper limit of normal (ULN).
- ALT $\geq 3 \times$ ULN and total bilirubin $\geq 2 \times$ ULN or international normalised ratio (INR) of ≥ 1.5 , as per the guidelines for acute liver failure (if a subject meets that withdrawal criterion, serum bilirubin fractionation should be performed).
- ALT $\geq 3 \times$ ULN if associated with the appearance or worsening of rash or hepatitis symptoms (fatigue, nausea, vomiting, right upper quadrant pain or tenderness, fever, rash or eosinophilia). Subjects who have ALT $\geq 3 \times$ ULN and $< 5 \times$ ULN, and total bilirubin $< 2 \times$ ULN, who do not exhibit hepatitis symptoms or rash, can continue in the study (and continue receiving trial medication) as long as they can be monitored weekly until liver chemistries return to within baseline values.
- FEV₁ or FVC of $< 80\%$ predicted or a decrease of $> 20\%$ from baseline
- Peripheral arterial oxygen saturation (SpO₂) of $< 94\%$

Subjects who meet the above criteria will be considered discontinued from dosing. However, the investigator may ask the subject to continue their participation in the study so they can be monitored for safety, PK and immunogenicity, or the investigator may withdraw the subject from the trial.

Subjects will be informed before they agree to take part in the trial that, if they withdraw or are withdrawn:

- the investigator will stop collecting information about them; and
- they can ask the investigator to destroy any identifiable samples taken from them.

The investigator will ask withdrawn subjects to provide written consent to a follow-up examination, to check that they have come to no harm as a result of taking part in the trial. Provided that the subject agrees, they will undergo, at withdrawal from the trial (or as soon as possible afterwards), the standard medical examination and laboratory tests which they would have undergone had they completed it. The investigator will record in the case report form (CRF) the results of the follow-up examination of withdrawn subjects, if they give their consent for that.

9.4.3 *Replacement of withdrawn subjects*

Withdrawn subjects will be replaced at the discretion of the sponsor and investigator. Replacements for withdrawn subjects will receive the treatment(s) intended for the withdrawn subject.

10 *Treatments*

10.1 *Treatments administered*

Part A: subjects will receive a single dose of Neumifil or placebo.

Part B: subjects will receive once-daily doses of Neumifil or placebo for 7 days.

All doses will be administered intranasally using an Aptar liquid delivery system. Each dose will consist of nasal drops/spray administered as a maximum volume of 0.5 mL to each nostril. Subjects must lie supine for 5 min after dosing. Further details will be provided in a separate manual.

Fasting requirements are described in section 11.

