Women of childbearing potential must use a highly effective method of contraception with low-user dependency during the trial, and for up to one month after the final follow up visit. They must have been using that method for at least 28 days before the start of the trial. Highly effective methods of contraception include:

- Progestogen-only hormonal contraception implants associated with inhibition of ovulation
- Intrauterine device (IUD)

- Intrauterine hormone-releasing system (IUS)
- Bilateral tubal occlusion or ligation
- Vasectomised partner (with surgical success confirmed by medical assessment)

A woman is considered to be of non-childbearing potential if she meets one of the following criteria:

- is post-menopausal (the last menstrual period was at least 12 months ago, and Follicle Stimulating Hormone (FSH) test at screening confirms post-menopausal status)
- has no uterus, ovaries or fallopian tubes

Women who are taking HRT must use contraception (as described above) during the trial unless prescribed following bilateral oophorectomy, hysterectomy or salpingectomy.

Combined or progesterone-only hormonal contraception associated with inhibition of ovulation (oral, intravaginal, transdermal or injections) are not allowed.

Subjects who practise true abstinence or who only have same-sex relationships need not use contraception, provided it is in line with their preferred and usual lifestyle (note: periodic abstinence [eg calendar, ovulation, symptothermal, and post-ovulation methods] and withdrawal are not acceptable methods of contraception). Should any such subject stop practising true abstinence, they must use contraception as described above.

12 Procedures and observations

Only subjects who meet all the inclusion and no exclusion criteria will be eligible for enrolment into the trial (see section 9). Each subject will be allocated a unique trial number (see section 10.5).

Additional time points may be introduced, and changes to time points may be made, in accordance with section 12.2.

The following assessments will be made at the timepoints given in sections 12.1.1 (Part A) and 12.1.2 (Part B).

Safety and tolerability

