6. ECGs will be recorded at screening; before and at 2.5 h after dosing on Days 1 and 7; and at follow-up. Triplicate recordings (to at least 2 min apart) will be made at screening; single recordings will be done at all other time points. Recordings should be made with subjects in a supine position, after resting for 5 min.
7. Laboratory safety tests consist of biochemistry, haematology and urinalysis in serum. They will be done at screening; on Day –1; at 24 h after dosing on Day 1; on Day 8; at the outpatient visit; and at follow-up. Subjects should fast for \geq 8 h before laboratory safety tests at screening, admission (Day –1), and follow-up.
8. Pregnancy tests in women of child-bearing potential only.
9. FSH tests in post-menopausal women at screening only.
10. FEV₁ and FVC will be measured at screening; at 4, 8, 12 and 24 after dosing on Days 1 and 7; at the outpatient visit; and at follow-up.
11. If a subject develops symptoms of COVID-19, ad hoc SARS-CoV-2 infection tests will be done.
12. Self-assessment nasal tolerability questionnaires will be completed at 1 and 12 h post dose after each dose of Neumifil.
13. Once-daily intranasal doses of Neumifil.
14. Blood samples for assay of Neumifil will be taken:
 - before and at 1, 2, and 3 h after dosing on Days 1 and 7
15. Blood samples for assay of Neumifil ADAs will be taken before dosing on Day 1, and at follow-up.
16. Nasal wick samples will be taken before the evening meal on Day –1, or not less than 2 h after food at all timepoints.

When more than one procedure is scheduled at a specific time point, procedures should be done in the following order: ECG, vital signs, blood samples (at the scheduled time), then spirometry. Blood sampling should be done on time. Other procedures should be done as close as possible to the scheduled time point.

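### Part B stopping rule: on the default 7-day course no scheduled ALT, FEV₁ or FVC reading can withhold a dose for effects of doses 2–6, and INR is an unscheduled trigger that clashes with the continuation clause

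*Combined protocol and SAP*

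**What the plan says.** Section 9.4.2 applies to Part B only: "A subject who meets any of the following criteria will receive no further doses". Its criteria include ALT thresholds, FEV₁ or FVC below 80% predicted or down more than 20% from baseline, and SpO₂ below 94%.

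The default regimen is in section 10.1: "subjects will receive once-daily doses of Neumifil or placebo for 7 days". Section 12 makes the schedule govern: "The following assessments will be made at the timepoints given in sections 12.1.1 (Part A) and 12.1.2 (Part B". After the Day –1 sample, note 7 of section 12.1.2 places laboratory tests "at 24 h after dosing on Day 1; on Day 8; at the outpatient visit; and at follow-up". After screening, note 10 places spirometry "at 4, 8, 12 and 24 after dosing on Days 1 and 7; at the outpatient visit; and at follow-up".

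One liver criterion combines ALT ≥ 3 × ULN with bilirubin ≥ 2 × ULN "or international normalised ratio (INR) of" 1.5 or more. The same bullet adds that, "if a subject meets that withdrawal criterion, serum bilirubin fractionation should be performed". The next bullet says that subjects with ALT from 3 to below 5 × ULN and bilirubin below 2 × ULN, "who do not exhibit hepatitis symptoms or rash, can continue in the study (and continue receiving trial medication"), provided weekly monitoring is possible. That sentence does not mention INR.

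**The concern.** The rule protects a subject by withholding the doses still to come. If the schedule is followed as written, a symptom-free change in ALT or lung function that develops over doses 2–6 would first be measured after the last dose, when nothing is left to withhold.

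Spirometry carries more weight than ALT. Section 6.2.5 reports abnormal respiratory sounds at all dose levels in the 28-day rat study, with inflammatory changes in larynx, trachea, bronchi and bronchioles at the 2 highest, although the animals recovered fully within 2 weeks. Section 6.2.3 says that no standalone respiratory safety study was done. For ALT, no hepatic signal is cited and systemic exposure is expected to be very low.

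The INR problem is of another kind. INR helps decide whether a criterion is met, but nothing schedules it, and two bullets give opposite instructions for the same subject. Bilirubin fractionation is also outside Table 7, but it follows once the criterion is met and does not determine it.

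**Working it through.** **Inputs.** Doses: section 10.1, dose k at 24 × (k − 1) h for k = 1 to 7, so 0, 24, …, 144 h. Readings: section 12.1.2, note 5 (vital signs, including SpO₂), note 7 (laboratory tests) and note 10 (spirometry). Tolerances: 15 min either way for a dose (section 10.6) and for a reading after 4 h and up to 24 h (Table 6).

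**The plan's own count.** Note 7 gives screening, Day –1, 24 h after dose 1, Day 8, outpatient visit and follow-up, which is 6. Table 9 plans 6 haematology and 6 biochemistry tests. They agree, so no further sample is planned.

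**Scheduled readings taken after dose k and no later than a remaining dose.**

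| Dose k | ALT | FEV₁/FVC | SpO₂ |
|---|---|---|---|
| 1 | 1 (24 h) | 4 (4, 8, 12, 24 h) | 6 (2, 4, 8, 12, 24 h; pre-dose Day 7) |
| 2 to 6, each | 0 | 0 | 1 (pre-dose Day 7; can withhold dose 7 only) |
| 7 | 0 | 0 | 0 |

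**Gaps between consecutive scheduled readings.**
- Laboratory tests: 168 − 24 = about 144 h.
- Spirometry: 148 − 24 = 124 h.
- SpO₂: 144 − 24 = 120 h, or 142.5 − 24 = 118.5 h at the earliest permitted pre-dose time.

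Doses inside the gap: for ALT and spirometry, 6 if the 24-h reading precedes dose 2 and 5 if it follows; for SpO₂, 5 or 4. Days 3–6 (4 of the 7 dosing days) have no scheduled ALT, FEV₁/FVC or SpO₂.

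**Edge of the tolerances.** With dose 2 given 15 min early and the 24-h reading 15 min late, the reading falls 15 + 15 = 30 min after dose 2. That is the most the schedule can see of doses 2–6 for ALT and spirometry while doses remain.

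**Two checks on the schedule text.** Table 6 has a pre-dose row for Days 2–6, but it only sets a time window, and notes 5, 7 and 10 place no test on Days 3–6. In the extracted grid the later laboratory mark lies in the column of the Day 7 dose. The SARS-CoV-2 test and nasal wick, which section 7.2.2 dates to Day 8, lie in the same column, so the column does not settle the day and note 7 (Day 8) is used. If the mark did mean pre-dose Day 7, ALT would have 1 reading, able to withhold dose 7 only, with a gap of about 120 h. Spirometry would stay at 0.

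**INR.** INR is absent from Table 7, the tube list in section 12.4, the section 12.1.2 schedule and Table 9, so 0 tests are planned. Test case: ALT 4 × ULN, bilirubin 1 × ULN, INR 1.6, no symptoms or rash.
- Stop, read as ALT ≥ 3 and (bilirubin ≥ 2 or INR ≥ 1.5): met.
- Stop, read as (ALT ≥ 3 and bilirubin ≥ 2) or INR ≥ 1.5: met.
- Continue, ALT ≥ 3 and < 5, bilirubin < 2, no symptoms or rash: met, if weekly monitoring is possible.

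The subject falls under both instructions, however the and/or is read.

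**Subjects.** 3 groups × 6 = 18 on Neumifil in B1–B3; 3 × 8 = 24 including placebo.

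**The case against.** The strongest answer is that section 9.4.2 is conditional: it says what happens when a criterion is met and promises no testing frequency. It can act on first-24-h readings, the pre-dose Day 7 SpO₂, a related SAE, or an unscheduled test under sections 12.2 and 12.3. All of that is true. But unscheduled tests are discretionary, and nothing prompts one in a symptom-free subject, where numeric thresholds are most useful.

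The rule may also have been written for other regimens. Section 8.5.3 allows up to 14 days and twice-daily dosing. In a longer course the Day 7 spirometry and Day 8 laboratory tests would precede remaining doses; with twice-daily dosing, some Day 7 spirometry could precede the evening dose. This stands, and it limits the timing finding to the default regimen, which is the one planned.

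Several facts limit the severity. Part B daily doses may not exceed a Part A single dose that caused no safety concerns. The 2.8 mg cap at 60 kg is 2.8/60 = 0.047 mg/kg, about 54-fold below the rat NOAEL (2.5 mg/kg/day) and 35-fold below the monkey NOAEL (1.65 mg/kg/day). The 28-day monkey study showed no change in respiratory signs and all its plasma concentrations were below the limit of quantification; rat intranasal bioavailability was below 5%. Subjects are resident, are asked about AEs and complete a nasal questionnaire after each dose. The Safety Review Group sees laboratory tests and FEV₁ before escalating, which protects the next group but not a subject in mid-course.

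On INR, one can argue that the mandatory stop list overrides a permissive sentence and that INR can be a reflex test. Either may be intended, but the protocol says neither.

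**Conclusion.** The concern holds, as a minor point. For 7 once-daily doses at nominal times, and taking note 7 as the authority for the Day 8 laboratory test, the number of scheduled readings able to withhold a dose because of doses 2–6 is 0 for ALT, 0 for FEV₁/FVC and 1 for SpO₂. The spirometry result does not depend on how the grid is read. The timing part is a mismatch between a rule and its schedule rather than a contradiction in wording. The INR part is a contradiction: a trigger with no planned test, and one subject under two opposite instructions. The low rating reflects the dose cap, the low exposure and the inpatient stay.

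**What to change.** Reconcile sections 9.4.2 and 12.1.2 and Tables 7 and 9 so that each stopping criterion has a scheduled measurement that can trigger it while doses remain. Alternatively, state that the ALT and FEV₁/FVC criteria are not meant to act on effects of doses 2–6. State where the INR value comes from, and reconcile the INR alternative with the continuation clause so that no subject falls under both. The days, tests and thresholds are for the protocol team; none is proposed here.

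The cost is a text or schedule amendment. Subjects are resident from Day –1 to Day 8, and every procedure except INR is already in use. Spirometry needs no blood. If the team chose to add a biochemistry sample, it would take 3.5 mL (Table 9), or 3.5/80 = 4.4% of the extra allowance in section 12.5. The documents give no volume for an INR sample.
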